Short Title / Study ID	New technologies in the rehabilitation of chronic stroke 2018-01214
Protocol Version and Date	Version 02, September the 12 th 2018
Trial registration	clinicalTrials.gov: NCT03641651
Study category and Rationale	Other clinical study Category A The phase of development covered by this study pertains to the efficient application of a combination of commercially available rehabilitation technology, corresponding to phase III.
Background and Rationale	Limitations in the performance of activities are a frequent consequence of a cerebro-vascular stroke. Partial paresis, abnormal muscle tone and deteriorated coordination are among others reasons for these deficits. From rehabilitation and motor (re-)learning studies it is known that skilled movements can be trained. The success of such training depends on the context of training, the motivation of the patients and the training intensity. These factors can be tailored and controlled with the use of rehabilitation technologies such as robotics or audio-visual feedback devices. However, up to now only sparse evidence and experience is available on the efficient application of such devices.
Objective(s)	The objective of the current study is to develop and investigate training concepts involving rehabilitation technology, which aim at exploiting the potential for regaining the ability to perform skilled movements by maximizing training intensity while keeping the motivation of patients high. The evaluation focuses on feasibility and cost-benefit analyses.

Outcome(s)	
 • Variables from the devices such as 
 ◦ number of trainings ◦ training duration, number of repetitions ◦ support ◦ success rate (for game-like tasks) • Patient related outcomes 
 ◦ Lower extremities ◦ Upper extremities ◦ Functional independence Measurement (FIM) ◦ Questionnaire for the patients covering: 
 ▪ motivation ▪ adherence ▪ perceived support (Fühlen sie sich gut betreut) ▪ desire to continue such a training ▪ subjective rating of the training modalities (which was the best, which was the most interesting) • Adverse events 
 ◦ Medical complications ◦ organizational challenges • Economic variables 
 ◦ Descriptives (quantities, prices, operational procedures in the use of the technology) ◦ Efficiency analysis ◦ Reimbursement
Study design	Multicenter-single arm feasibility study
Inclusion / Exclusion criteria	
Inclusion:
 
 • Patients with residual hemiparesis after cerebrovascular accident • Up to 12 months after the event • Primary rehabilitation terminated • Able to cognitively comprehend the aim of the project • General health condition allows for intensive rehabilitative training with limited supervision i.e. clearance of responsible physician • Understand written and spoken German language 
Exclusion:
 
 • Presents with contraindication for the training with the respective devices

Study Intervention	
 • Series of tailored rehabilitative trainings with the use of new technology which provide feedback and allow for a targeted, intensive and dense training. • With limited supervision based on patients preconditions and therapy device (e.g. patient/therapist ratio= 3/1). • A training series lasts four weeks and comprises 3-5 training-days per week. Maximum training break of 7 days. A minimum of five blocks of training with duration of 45 min per training day each are foreseen. 
The training can take place in an in- or outpatient setting

Reference Intervention	Not applicable
Number of Participants with Rationale	As this study is a feasibility study: N= 20 (five subjects for every clinical site).
Study Duration	Thirty months (30m) in total.
Study Schedule	11/2018 First-Participant-In (planned) 05/2020 of Last-Participant-Out (planned)
Investigator(s)	
[name] Rehakliniken Zihlschlacht [name] [name] [contact] [contact]
 
[name] Reha Rheinfelden [name] [name] [contact] [contact]
 
[name] Kliniken Valens Rehabilitationszentrum [name] [contact] [contact]
 
[name] Klinik Lengg AG [name] [name] [contact] [contact]

Study Centre(s)	see above

Statistical Considerations	Descriptive analysis Pre-post comparisons of patient-related outcomes
GCP Statement	This study will be conducted in compliance with the protocol, the current version of the Declaration of Helsinki, the ICH-GCP as well as all national legal and regulatory requirements.

LIST OF ABBREVIATIONS

AE	Adverse Event
ClinO	Clinical Trial Ordinance (KlinV)
CRF	Case Report Form
eCRF	Electronic Case Report Form
GCP	Good Clinical Practice
ICH	International Council on Harmonization
ISF	Investigator Site File
PI	Principal Investigator
SAE	Serious Adverse Event
SDV	Source Data Verification
SNCTP	Swiss National Clinical Trial Portal
SOP	Standard Operating Procedure
TMF	Trial Master File

1.4 Statistician (Biometrician)

NA, feasibility study

2 ETHICAL AND REGULATOR ASPECTS

Before this study will be conducted, the protocol, the proposed participant information and consent form as well as other study-specific documents will be submitted to a properly constituted Competent Ethics Committee (CEC) in agreement with local legal requirements, for formal approval.

The decision of the CEC concerning the conduct of the study will be made in writing to the Sponsor-Investigator before commencement of this study. The clinical study can only begin once approval from the CEC has been received.

2.1 Study Registration

The study will be registered in the Swiss National Clinical Trials Portal (SNCTP) and in the international trial registry ClinicalTrials.gov (clinicaltrials.gov). Registration number: NCT03641651

2.2 Categorization of the Study

Category A: the intervention is clinical standard.

2.3 Competent Ethics Committee (CEC)

The ethical committee of the Canton Zurich is regarded the lead ethical committee. Due to the multicenter status of this trial, the ethical committees of St. Gallen (EK Ostschweiz) and Nordwest-and Zentralschweiz (EKNZ) are also involved and will be asked for approval.

The reporting duties and allowed time frame are respected. No substantial amendments are made to the protocol without prior CEC approval, except where necessary to eliminate apparent immediate hazards to study participants. Premature study end or interruption of the study is reported within 15 days. The regular end of the study is reported to the CEC within 90 days, the final study report shall be submitted within one year after study end. Amendments are reported according to chapter 2.9.

2.4 Ethical Conduct of the Study

The study will be carried out in accordance with principles enunciated in the current version of the Declaration of Helsinki, the guidelines of Good Clinical Practice (GCP) issued by ICH, and Swiss competent authority's requirements.

CEC will receive annual safety and interim reports and be informed about non-substantial amendments, the course of the study, and the study stop/ end in agreement with local requirements.

2.5 Declaration of Interest

There is no conflict of interest by any person involved in conducting this clinical trial.

2.6 Participant Information and Informed Consent

The investigator must explain to each participant the nature of the study, its purpose, the procedures involved, the expected duration, the potential risks and benefits and any discomfort it may entail. Each participant must be informed that the participation in the study is voluntary and that he/she may withdraw from the study at any time and that withdrawal of consent will not affect his/her subsequent medical treatment.

The participant must be informed that his/her medical records may be examined by authorized individuals other than their treating physician.

All participants for this study will be provided a participant information sheet and a consent form describing this study and providing sufficient information for participants to make an informed decision about their participation in this study.

The participant information sheet and the consent form will be submitted with the protocol for review and approval for the study by the CEC. The formal consent of a participant, using the approved consent form, must be obtained before that participant is submitted to any study procedure.

The participant should read and consider the statement before signing and dating the informed consent form, and should be given a copy of the signed document. The consent form must also be signed and dated by the investigator (or his designee) and it will be retained as part of the study records.

2.7 Participant Privacy and Confidentiality

The investigators are liable to treat the entire information related to the study and the compiled data strictly confidentially. Any passing-on of information to persons that are not directly involved in the study must be approved by the owner of the information.

Data generation, transmission, archiving and analysis of personal data within this study, strictly follows the current Swiss legal requirements for data protection. Prerequisite is the voluntary approval of the Participant given by signing the informed consent prior start of participation of the clinical trial.

Individual participant medical information obtained as a result of this study is considered confidential and disclosure to third parties is prohibited. Participant's confidentiality will be further ensured by utilizing participant identification code numbers to correspond to treatment data in the computer files.

Such medical information may be given to the participant's personal physician or to other appropriate medical personnel responsible for the participant's welfare, if the patient has given his/her written consent to do so.

Data generated as a result of this study are to be available for inspection on request by the monitors and by the CEC.

2.8 Early Termination of the Study

The Sponsor-Investigator may discontinue the study prematurely according to certain circumstances:

- ethical concerns,
- insufficient participant recruitment,
- when the safety of the participants is doubtful or at risk, respectively,
- alterations in accepted clinical practice that make the continuation of a clinical

- trial unwise,
- early evidence of benefit or harm of the experimental intervention

2.9 Protocol Amendments

Substantial amendments (significant changes) are only implemented after approval of the CEC.

Significant changes to be authorised by the CEC are the following:

- changes affecting the participants' safety and health, or their rights and obligations;
- changes to the protocol, and in particular changes based on new scientific knowledge which concern the trial design, the method of investigation, the endpoints or the form of statistical analysis;
- a change of trial site, or conducting the clinical trial at an additional site; or
- a change of sponsor, coordinating investigator or investigator responsible at a trial site.

Under emergency circumstances, deviations from the protocol to protect the rights, safety and well-being of human participants may proceed without prior approval of the sponsor and the CEC. Such deviations shall be documented and reported to the sponsor and the CEC as soon as possible.

All Non-substantial amendments are communicated to the CEC within the Annual Safety Report (ASR).

3 INTRODUCTION

3.1 Background and Rationale

Damage of the neurological system, because of illness or injury, affects over a billion people worldwide [1]. This damage can, amongst other consequences, lead to motor impairment, which necessitates rehabilitative treatment. Rehabilitation has been defined by the World Health Organization (WHO) as “active process by which those affected by injury or disease achieve a full recovery or, if a full recovery is not possible, realize their optimal physical, mental and social potential and are integrated into their most appropriate environment” [2]. Literature shows, that intensive training is required to exploit the full potential of recovery. There is in fact overwhelming evidence that more intensive training leads to better rehabilitation outcomes in individuals with stroke [3-14] and reduces hospital readmission rates [15]. However, today, clinical reality looks rather different. Many individuals with motor impairments are discharged from rehabilitation considerably short of attaining their optimal potential. Rather than receiving therapy until their potential is reached, they are discharged when it is considered safe by the third party payers [16]. Actual therapy time during a regular day at a rehabilitation hospital is generally very limited, mostly due to management decisions, lack of structured organization and inefficient use of resources [17, 18]. In four European rehabilitation centers, individuals with stroke received between one and three hours of therapy per day, while over 72% of time was spent with non-therapeutic activities [17]. This has consequences, as these authors also were able to show that patients in centers with less therapy time per day have less functional recovery than those who are treated in centers that provide more therapy time per day [18]. In addition, within a session of conventional therapy, dosage is generally rather low, even during inpatient rehabilitation. For example, Hayward et al. describe that the dose of activity-related arm training only adds up to an average of 4min and as little as 23 repetitions per therapy session during inpatient rehabilitation [19]. Lang et al. found an average number of repetitions per session of 32 for the upper extremity and of 357 for the lower extremity [20].

Individuals post stroke also make significantly less use of their upper extremities throughout the rest of their day during inpatient rehabilitation. While able-bodied control persons use their arms during 8-9hrs per day, individuals with stroke during inpatient rehabilitation use their more affected arm during 3.3 hrs and their less affected arm during 6 hrs per day [21]. This non-use leads to negative plasticity and further impairment [22].

So, while it is certainly possible to intensify therapeutic treatments during inpatient rehabilitation [12, 18], it is challenging for many reasons and often not done. Needless to say that this less than optimal amount of therapy provided results in large amounts of untouched recovery potential. Out of the roughly 15 million people worldwide who experience a stroke each year, 5 million live with permanent disability [1]. The Framingham study for example showed that of all stroke survivors, 20% remain dependent in their mobility [23]. Clearly, this dependency, as well as other under-treated impairments lead to tremendous costs throughout the person’s lifetime [24-27]. For Medicare users in the United States for example, while mean rehabilitation length of stay after an acute stroke was only 14.6 days, readmission rate to the hospital was 12.7% within the first 30 days after discharge from rehabilitation [28]. In Europe, the total cost resulting from strokes was 37.4 billion in 2010 [29]. In Switzerland, in 2014,

25.8% of health costs were spent on acute inpatient treatment, while only 1.7% were spent on inpatient rehabilitation. Outpatient physical therapy only added up to 1.4% of the total health costs [30].

There is a desperate need for affordable solutions to provide our patients the intensity of therapy necessary to optimally exploit their potential for recovery. Finding such a solution must include dialog between all the stakeholders, i.e. patients, clinicians, technological solution providers and insurers. The Swiss Rehab Tech Initiative aims to do exactly that. It provides a platform where all involved parties come together. The initiative is now ready to test a model solution in the clinic.

3.2 Study Intervention and Indication

In a first step, the feasibility of the intervention aims to establish efficient settings in four trailblazer clinics. This will enable them to provide intensive therapy to the patients in accordance with the study protocol. While these settings are integrated into the clinical routine, we will be able to collect data to get some first insight into economic and functional data required to calculate changes in socioeconomic costs.

3.3 Clinical Evidence to Date

Suitable solutions include advanced technology, such as electromechanically assisted gait and arm trainers, which is one way to allow reaching high training intensities [31, 32]. These devices take the physical burden from the therapists, thus allowing training duration to be limited by the patient's capabilities rather than by exhaustion of the therapists. With the assistance of such devices, participants in one study performed up to over 600 functional arm movements per session [33]. Another study describes walking distances of up to 2000m (roughly 3300 steps) per session in an individual with spinal cord injury [34]. Technology assisted training has received considerable attention over the past years. This is reflected in a large number of published research studies. Numerous individual trials and several systematic reviews [35-38] have shown the positive effects of robotic assisted gait training, as well as of technology assisted training of the upper extremity [35, 36, 38, 39]. Cochrane Reviews showed that every fifth gait dependency could be prevented if patients received electromechanically assisted gait training in addition to their regular therapy program [40] and that electromechanical and robot-assisted arm training leads to improvements in activities of daily living and arm function [41] in individuals post stroke. Similar to physical therapy in general, it was also shown for technology assisted gait training that more intensive training programs lead to improved outcomes [42].

All these studies have shown that it is in fact possible to improve outcomes through intensifying training paradigms.

3.4 Justification of Study Intervention

Treatment intensification so far has often taken place within a research environment and with the corresponding reimbursement through grants or other sources. In order to show the effect under clinical every day conditions and reimbursement situations, efficient settings have to be integrated into rehabilitation institutes and their effect on

patient outcome as well as economic parameters have to be shown. Investing into new technologies to provide efficient settings and delivering high intensive therapy as requested by clinical evidence is currently the sole responsibility of healthcare providers. It is not reimbursed either through support of investments or reimbursement. Specifically with certain reimbursement models, such as diagnosis related groups, there is no incentive for rehabilitation institutions to invest in such therapy models and provide more therapy for their patients.

3.5 Explanation for Choice of Comparator Intervention

Not applicable, pilot study without control intervention

3.6 Risk / Benefits

As the technological devices under study have already been certified as medical devices and are currently used in involved clinics, there are no adverse risks to be expected. To examine the benefits of this intervention by using specific outcome measurements is part of this research project. Further aspects are discussed under point 4.4 (Safety outcomes).

3.7 Study Population

The study aims to target on patients with a residual hemiparesis after a cerebrovascular accident up to 12 month ago. The primary rehabilitation has terminated. Their general health conditions should be stable to allow nearly daily intensive rehabilitation. Patients should cognitively and educationally be able to communicate verbal and non-verbal in German language. Specific inclusion and exclusion criteria are specified under [7.1](#). Each involved clinical site aims to include five patients. The enrolment procedure will be iterative with one or two clinics starting the recruitment. A total of twenty (n=20) patients are aimed to be enrolled.

4 STUDY OBJECTIVES

4.1 Overall Objective

This feasibility project aims to establish an efficient setting for intensive rehabilitation with new technology in four trailblazer clinics. This will enable them to provide intensive therapy to the patients in accordance with the study protocol. If this setting is integrated into the clinical routine, we will be able to collect data to get some first insight into economic and functional data required to calculate changes in socioeconomic costs.

4.2 Primary Objective

Develop and investigate the feasibility of a rehabilitative training program adopting new technologies, which focuses on scientifically based intensity and efficiency.

4.3 Secondary Objectives

Describe economic costs of the program.

Document and evaluate functional changes in response to the training.

4.4 Safety Objectives

All medical devices will be used as indicated. Involved physiotherapists will be trained in using the devices and supervising the training. Every clinic has its emergency plan, which will be applied in case of need

Participants will be supervised permanently during the intervention. No adverse events (AE) or serious adverse events (SAE) are expected to occur. However, participating subjects might complain about tiredness or muscle soreness due to the intensive intervention, which will be recorded on the case report form (CRF).

All adverse (AE) and serious adverse events which will be defined later (Point 10) whether related or unrelated will be recorded in the case report form (CRF). The CEC will be informed of any SAE within 15 days.

4.5 Primary Outcome

The primary outcome is to assess the feasibility of planned trainings. Every training and training day will be described in terms of

- devices used,
- duration of training,
- training mode (passive, active or resistive) and
- feedback given by the device.

The specific interest is the adherence of the patients:

- to planned trainings in terms of planned vs. actually performed training-days and training intensity.

- the subjectively perceived effort by the patients to perform the trainings will be recorded on a visual analogue scale (VAS).
- the subjectively perceived effectiveness will be recorded by using the “Patients Global Impression of Change” = PGICS)

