6.4 Criteria for Withdrawal/ Discontinuation of Participants

Patients not willing to adhere to the protocol will not be included. For included patients who, while having already attended some session but are not able to complete the six weeks program within the intensity planned, a tailored reduction of intensity in terms of days, hours per days and/or sessions per day is considered. A maximum training break of 7 days is foreseen

Patients who withdraw before the start of the study will be replaced.

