8.3.3 Start of training

In the beginning of each training day, patient and therapist will plan the day including sessions, and devices to be used.

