10 STATISTICAL METHODS

10.1 Hypothesis

Not applicable, as this study is a feasibility study. **Determination of Sample Size**

Twenty patients, five at each site are planned to be enrolled. A sample size calculation is not applicable for this feasibility study.

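### Adherence carries the primary feasibility question, but it has no patient-level definition, no target and no stated denominator once a plan is reduced

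*Combined protocol and SAP*

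**What the plan says.** Section 4.2 makes the feasibility of the training programme the primary objective. Section 4.5, repeated in 8.2.1, turns this into the outcome: "The primary outcome is to assess the feasibility of planned trainings". Two lists follow. The first is descriptive ("Every training and training day will be described in terms of"): device, duration, mode and feedback. The second opens with "The specific interest is the adherence of the patients" and holds three items: adherence "to planned trainings in terms of planned vs. actually performed training-days and training intensity", perceived effort on a visual analogue scale, and the patient's global impression of change. No level is attached to any of the seven items (4 + 3).

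Section 10.1 says of a hypothesis: "Not applicable, as this study is a feasibility study". The sample is five patients at each of four sites, without a calculation. Section 10.3 calls the analysis of intervention-related outcomes primarily descriptive. Section 10.3.1 adds a chi-square for adherence rates and names no groups, reference rate or significance level.

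On the plan itself, 7.3 and 8.3.2 have all days and sessions scheduled in advance and entered in the CRF at baseline. For a patient who cannot keep to the intended intensity, 6.4 says "a tailored reduction of intensity in terms of days, hours per days and/or sessions per day is considered", and 7.2.1 allows the same adaptation. Section 10.4 keeps all patients in the primary analysis.

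**The concern.** A feasibility study needs no hypothesis test. It does need to say beforehand what it would accept as feasible. Here adherence is the natural deciding measure, but three things are open: what makes one patient adherent, how many such patients are enough, and which plan performed training is divided by. A chi-square cannot settle the second point, because in a single-arm trial it needs either a reference rate or groups to compare, and neither is stated.

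The denominator gives the problem a direction. A reduction under 6.4 can only make the plan smaller. Adherence measured against the reduced plan is therefore never lower, and usually higher, than adherence to the programme first planned. The patients affected are those who found the planned intensity too much, which is what a feasibility study sets out to learn. At stake is whether the primary objective gets an answer whose standard was fixed before the results were known.

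**Working it through.** **1. The plan's own figure.** 4 sites × 5 patients = 20. This reproduces as arithmetic. No alpha, power, target rate or effect size is given, so no power or precision calculation can be reproduced.

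**2. Search for a criterion.** The sections that could hold one are:
- 4.5 and 8.2.1: seven items, no level.
- 10.1 and the sample size paragraph: no hypothesis, no calculation.
- 10.3 and 10.3.1: descriptive statistics, and a chi-square without a comparator.
- 6.4, 7.1.1 and 10.4: a seven-day limit on training breaks. This governs individual conduct and entry to the secondary analysis. It is not a study-level criterion.
- 7.3: refers to a minimum programme in 6.4, but 6.4 gives no number of days or sessions.

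Study-level feasibility thresholds found: 0.

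**3. How far the denominator can move.** Section 7.1.1 gives four weeks at 3–5 days per week: 4 × 3 = 12 to 4 × 5 = 20 training-days. Section 6.4 speaks of six weeks; if the same weekly frequency applies (an assumption), 6 × 3 = 18 to 6 × 5 = 30. For a patient who performs 12 days:

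| Planned days | Adherence |
|---|---|
| 12 | 12/12 = 100% |
| 18 | 12/18 = 67% |
| 20 | 12/20 = 60% |
| 30 | 12/30 = 40% |

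Sessions behave in the same way. At five sessions per day (7.1.1), a 20-day plan holds 100 sessions and a plan cut to 12 days holds 60. Performing 60 is 60/60 = 100% of the reduced plan and 60/100 = 60% of the baseline plan.

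**4. What 20 patients could support.** Class each patient as adherent or not. The cut of 16/20 and the true rates below are assumptions; the documents give none. Pass probability: P(X ≥ 16) = Σ C(20,k) p^k (1−p)^(20−k), for k = 16 to 20.

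| True rate p | P(pass) |
|---|---|
| 60% | 0.051 |
| 70% | 0.238 |
| 80% | 0.630 |
| 90% | 0.957 |

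Exact (Clopper–Pearson) 95% CI for 16/20: the lower limit is the 0.025 quantile of Beta(16, 5) = 0.563, and the upper limit is the 0.975 quantile of Beta(17, 4) = 0.943.

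Smallest cut with one-sided exact alpha of at most 0.05 at n = 20:

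| Unacceptable vs acceptable rate | Cut | Alpha | Power |
|---|---|---|---|
| 50% vs 80% | ≥15 | 0.021 | 0.804 |
| 60% vs 90% | ≥17 | 0.016 | 0.867 |
| 70% vs 90% | ≥18 | 0.036 | 0.677 |

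Twenty patients therefore separate rates about 30 points apart, but not reliably rates 20 points apart.

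**The case against.** A reader might infer that no result could ever count as not feasible, or that the trial would report near-full adherence whatever happened because 8.3.3 says "In the beginning of each training day, patient and therapist will plan the day including sessions, and devices to be used". The documents do not support either reading. Section 8.3, the parent of 8.3.3, ties each day's programme to the CRF training plan, and 7.3 and 8.3.2 set that plan at baseline. Daily planning is thus scheduling within the plan and does not replace it. Nor would patients who struggled disappear: 10.3.1 reports absolute training duration and perceived exertion, 8.2.4 collects reasons for withdrawal, and 10.4 keeps all patients in the primary analysis and examines drop-outs. A reduced dose would show in those data. It is also too strong to say that there is no leading measure, since adherence is singled out.

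A second objection is that the study never promises a yes or no. Section 4.2 speaks of developing and investigating, 4.1 of first insight, and 10.3 of description. That is fair as far as a formal test goes. But 5.1 also speaks of validating the programme, and a validation should say what it would accept. A third is that n = 20 gives a blunt rule, as the figures above confirm. This is a reason to publish the rule's pass probabilities, not to leave the standard open.

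What stands against these objections is narrower: no level, no patient-level definition, no comparator for the chi-square, and silence on the denominator after a reduction under 6.4 or 7.2.1.

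**Conclusion.** The concern holds in this limited form. The trial can describe adherence, but the meaning of the figure would be decided after it is seen. If reduced plans serve as the denominator, the figure is biased upward; in the example, a patient at 60% of the baseline plan is reported at 100%. How often this would happen cannot be derived, because the documents give no expected frequency of reductions. The CRF pages holding the plan are not part of the documents, so a denominator rule could exist there; the protocol text states none. The 16/20 cut and the true rates are illustrations only. The change is worth making, although the trial can run and report descriptively without it.

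**What to change.** In 4.5 (and 8.2.1) and 10.3.1, name one decision measure: the proportion of all enrolled patients who perform at least a pre-stated share of the sessions in the baseline CRF plan, whatever reductions follow. Sessions missed through reduction or drop-out count as not performed. Report the proportion with an exact 95% CI in place of the chi-square. State in advance the share, the number out of 20, and the rule's pass probabilities over a range of true rates. Keep the other items as description; adherence to the reduced plan can be shown beside the main figure.

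Two contradictions must be reconciled first, because the measure depends on them: the four-week programme in 7.1.1 against the six-week programme in 6.4, and the exclusion in 7.3 of patients below a minimum that 6.4 does not quantify against the inclusion of all patients in 7.4 and 10.4. Which version is intended is for the sponsor to say.

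No new data are needed: the plan is made at baseline and performed training is recorded daily. The cost is an amendment. Section 2.9 requires ethics committee approval for changes to endpoints or analysis, and 2.3 involves three committees. The sponsor also commits to a cut-off that the trial can miss.
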